6.1 COVID-19 Immunogenicity

The Duke NAb Laboratory for HIV and SARS-CoV-2 Vaccine Research and Development (Duke NAb Lab, PI: [name]) will assess the magnitude, kinetics and duration of neutralizing antibody responses against SARS-CoV-2 by using a validated assay in an environment that operates in compliance with Good Clinical Laboratory Practices (GCLP).

Neutralization of SARS-CoV-2 Spike-pseudotyped viruses will be assessed in 293T/ACE2 cells as described in SOP "CFAR02-A0026 Measuring Neutralizing Antibodies Against SARS-CoV-2 Using Pseudotyped Virus and 293T/ACE2 Cells." This assay has been formally validated and is part of Drug Master File # 26862 with the US Federal Drug Administration. Assay validation was performed with human serum samples and monoclonal antibodies using the D614G form of the Wuhan-1 Spike, which is the dominant form of Spike protein in the global epidemic. This assay has also been validated using B.1.351(246R) and B.1.1.529 (BA1) and may be validated for other newly emerged variants as needed.

Neutralization is measured by using lentiviral particles pseudotyped with SARS-CoV-2 Spike and containing a firefly luciferase (Luc) reporter gene for quantitative measurements of infection by relative luminescence units (RLU). SARS-CoV-2 Spike-pseudotyped viruses are prepared and titrated for infectivity by using mutated forms of an expression plasmid encoding codon-optimized full-length Spike of the Wuhan-1 strain (VRC7480) provided by Drs. [name] and [name] at the Vaccine Research Center, National Institutes of Health (USA). Mutations were introduced into VRC7480 by site-directed mutagenesis using the QuikChange Lightning Site-Directed Mutagenesis Kit from Agilent Technologies. All mutations were confirmed by full-length Spike gene sequencing. Pseudovirions are produced in HEK 293T/17 cells by transfection using Fugene 6 Transfection Reagent and a combination of Spike plasmid, lentiviral backbone plasmid (pCMV ΔR8.2) and firefly Luc reporter gene plasmid (pHR' CMV Luc) in a 1:17:17 ratio in Opti-MEM (Life Technologies). Pseudovirions are titrated

for infectious dose (TCID50) by making serial 3-fold or 5-fold dilutions in quadruplicate for a total of 11 dilutions in 96-well flat-bottom plates.

A pre-titrated dose of virus is incubated with 8 serial 5-fold dilutions of serum samples in duplicate in a total volume of 150 μ l for 1 hr at 37°C in 96-well flat-bottom culture plates. Cells are detached using TrypLE Select Enzyme solution, suspended in growth medium (100,000 cells/ml) and immediately added to all wells (10,000 cells in 100 μ L of growth medium per well). One set of 8 wells receives cells + virus (virus control) and another set of 8 wells receives cells only (background control). After 71-73 hrs of incubation, medium is removed by gentle aspiration and 30 μ l of Promega 1X lysis buffer is added to all wells. After a 10 minute incubation at room temperature, 100 μ l of Bright-Glo luciferase reagent is added to all wells. After 1-2 minutes, 110 μ l of the cell lysate is transferred to a black/white plate. Luminescence is measured using a GloMax Navigator luminometer (Promega). Neutralization titers are the serum dilution at which RLU are reduced by either 50% (ID50) or 80% (ID80) compared to virus control wells after subtraction of background RLU. Serum samples are heat-inactivated for 30 minutes at 56°C prior to assay.

For assay internal quality controls (IQC), a qualified positive control is tested on each assay plate (plate control). Assay run controls may consist of COVID-19 convalescent serum samples or SARS-CoV-2 vaccine recipients with high, medium and low ID50 and ID80 titers against the test virus, plus a normal human serum negative control. Levey-Jennings plots will be generated during testing and checked for violations of standards that are based on the Westgard Rules. Violations of the Westgard Rules are investigated in real-time.

7 STATISTICAL CONSIDERATIONS

In collaboration with the Cincinnati, Columbia, and Kaiser teams, the research team at Duke will oversee the statistical analysis. Data will reside on a secure Duke server maintained by Duke Health Technology Solutions (DHTS). For the study, a database will be developed and a data set for the study without personal identifiers will be made available to the CDC upon request. Duke statisticians will develop a comprehensive Statistical Analysis Plan. The summary points of the analysis plan are presented below.

7.1 Sample Size and Power Estimation

Because this is an observational study with no randomization of subjects into treatment groups, there will be no formal statistical power or sample size calculation.

7.2 Analysis Plan

7.2.1 Analysis Populations

There will be one study population named the Study Cohort. The Study Cohort includes any participant that was enrolled and received at least one dose of a COVID-19 vaccine.

7.2.2 Primary Objective

Primary Objective – To characterize the safety of authorized and recommended COVID-19 vaccines among children and adolescent participants

1) Tables will be produced that summarize each solicited local and systemic reactogenicity event by maximum classification (none, mild, moderate, and severe), as well as by moderate or severe through days 1-7 following COVID-19 vaccination for dose 1 and dose 2 or a booster dose. These tables will have the number and percentage for each classification and will be broken down by each site and across all sites. In addition, the number and percentage of participants with at least one moderate-to-severe local or systemic reactogenicity event will be described, as well as the proportion of participants with at least one severe local or systemic reactogenicity event. (POM 1, POM 2 and POM 3)

2) Tables will be produced that summarize each unsolicited adverse event by maximum classification (none, mild, moderate, and severe), as well as by moderate or severe through days 1-7 following COVID-19 vaccination for dose 1 and dose 2 or a booster dose. These tables will have the number and percentage for each classification and will be broken down by each site and across all sites (POM4).

3) Tables will be produced that summarize participants experiencing at least one serious adverse event or one AESI through the 29 days after dose 2 or a booster dose. This table will have the number and percentage for each outcome. Listings with the clinical narratives will also be provided. (POM5 and POM6)

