7.2.1 Analysis Populations.....	27
7.2.2 Primary Objective	27
7.2.3 Secondary Objective	28
7.2.4 Exploratory Objective.....	29
7.2.5 Safety Monitoring Plan.....	29
7.3 Data Management Plan.....	29
7.3.1 Research Electronic Data Capture (REDCap).....	29
7.3.2 Role of the CDC Investigators in the Project.....	30
8 HUMAN SUBJECTS	30
8.1 Human Participants Involvement, Characteristics, and Design	30
8.2 Sources of Material.....	31
8.3 Potential Risks and Benefits.....	31

8.4 Adequacy of Protection	31
8.4.1 ClinicalTrials.gov Requirements	31
9.0 HUMAN SUBJECTS.....	31
9.1.1 Vulnerable Subjects.....	31
9.1.2 Vulnerable Subjects Research	32
REFERENCES	33

PROTOCOL SUMMARY

Title:	A Prospective Observational Study to Evaluate the Safety of COVID-19 Vaccination in Children and Adolescents
Phase:	Phase 4
Population:	Up to 320 male or female children and adolescents \geq 5 years to < 16 years
Clinical Sites:	Four: Duke University (Lead); Cincinnati Children's Hospital (Contributing); Kaiser Permanente (Contributing); Columbia University (Contributing)
Study Duration:	24 months
Participant Duration:	Approximately 7 months
Description of Study Procedures:	
This is a prospective, observational study to evaluate the safety of COVID-19 vaccination in children and adolescents receiving vaccine as part of standard of care. Children and adolescents who have not received any previous COVID-19 vaccines will be enrolled with their first dose. Children and adolescents who have completed their primary vaccine series will enroll with their age-appropriate booster dose based on current FDA indications and CDC recommendations.
 
Injection-site (local) and systemic reaction data and unsolicited adverse events will be assessed on vaccination day and daily during the 7 days following each COVID-19 vaccination dose using either identical web-based or paper memory aids, depending on study participant preference.
 
At 3 sites, serum samples will be collected for optional assessment of antibody titers to COVID-19. Each participant who opts in will have baseline (within 3 days of vaccination) serologies obtained. Serum samples will also be collected for immunogenicity assessments at 28 (+7) days after dose 2 or a booster dose.
 
All participants will be followed for 181 days after the last study dose 2 or a booster dose for serious adverse events (SAEs) and adverse events of special interest (AESI).

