2 STUDY OBJECTIVES

Primary Objective (PO):

To characterize the safety of authorized and recommended COVID-19 vaccines among children and adolescent participants

Secondary Objective (SO):

To assess the safety of simultaneous administration of COVID-19 vaccine with other routinely recommended vaccines among children and adolescent participants

Exploratory Objectives (EO):

EO 1: To assess adolescent and parent perceptions of the COVID-19 vaccine recommendations and experience with receipt of the vaccine

EO 2: To assess the safety of COVID-19 vaccine stratified by baseline COVID-19 serostatus (positive versus negative) in a subset of child and adolescent participants

EO 3: To assess adverse events of special interest through 6 months after dose 2 of COVID-19 vaccine or a booster dose

EO 4: To assess serious adverse events through 6 months after dose 2 of COVID-19 vaccine or a booster dose

EO 5: To assess immune responses to SARS-CoV-2 antigens after COVID-19 vaccine

Primary Outcome Measures (POM):

POM 1: Proportion of participants with defined local or systemic reactogenicity events (stratified according to severity and in total) on days 1-7 after each dose of COVID-19 vaccine

POM 2: Proportion of participants with at least one severe (Grade 3) solicited local or systemic reactogenicity event on days 1-7 after each dose of COVID-19 vaccine

POM 3: Proportion of participants with at least one moderate-to-severe (Grade 2-3) solicited local or systemic reactogenicity event on days 1-7 after each dose of COVID-19 vaccine

POM 4: Proportion of participants with an unsolicited adverse event on days 1-7 after each dose of COVID-19 vaccine

POM 5: Proportion of participants with an adverse event of special interest through 29 days after dose 2 of COVID-19 vaccine or a booster dose

POM 6: Proportion of participants with at least one serious adverse event occurring through 29 days after dose 2 of COVID-19 vaccine or a booster dose and a description of the serious adverse events

Secondary Outcome Measure (SOM):

SOM: Assessment of primary outcome measures 1-6 in those receiving other routinely recommended vaccines simultaneously with each dose COVID-19 vaccine versus those receiving COVID-19 vaccine alone

Exploratory Outcome Measures (EOM):

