Visit 2, COVID-19 Vaccine Dose 2 (+ 3 Days) (Clinic or Phone Visit)

- Confirm receipt of second dose of COVID vaccine
- Record any AEs, AESIs, SAEs, and concomitant medications and vaccinations as described in **Section 5.5**.
- Record clinical data related to COVID-19 diagnoses
- Confirm preferred method of contact for follow-up (telephone, email, or text reminder)
- Review instructions for use of thermometer, ruler, and memory aid completion.

Visit 2a, Days 1 - 7 Days after dose 2 (Phone Visit)

- Subjects/parent/LAR will complete their memory aid via paper or electronic entry at approximately the same time each day for days 1-7, study staff will review subject-entered data within the database or by phone contact
- For participants using REDCap web-based system:
 - Study staff will send daily reminders to fill out the symptom diary
 - Record clinical data related to COVID diagnoses
 - Study staff will review REDCap system to confirm data capture and assess for any AE, AESIs, or SAEs on day 3 and 7 after vaccine

- If any missing values, reported hives, or Grade 3 or greater events occurred, the study staff will use phone contact to gather more information
- The second parental and adolescent (if applicable) survey will be administered on day 7 after vaccine
- For participants using paper diary:
 - Study staff will call participants on day 3 after vaccine as a reminder to fill out the symptom diary
 - The second parental and adolescent (if applicable) survey will be administered on day 7 after vaccine
 - Study staff will call participants on day 7 (+ 3 days) after vaccine
 - Record symptom diary
 - Record COVID-19 diagnoses
 - Record second parental and adolescent (if applicable) survey

Visit 3, 28 Days (window days 29-35) after COVID-19 Dose 2 (Clinic Visit or Phone Visit)

- Clinic visit for optional post-vaccination blood draw for immunogenicity studies
- If no blood draw, may be a phone visit
- Review concomitant medications and vaccinations.
- Solicit for the occurrence of any adverse events of special interest or serious adverse events.

Visit 4, 180 days (window Days 174 - 188) after Dose 2 (Phone Visit)

- Record any SAEs or adverse events of special interest as described in **Section 5.5**
- Obtain concomitant medication and vaccine use

Table 2 describes the schedule of study visits for children enrolling with their COVID-19 booster dose.

Table 2: Schedule of events: Booster Dose

Procedure	Visit 1	Visit 1a	Visit 2	Visit 3

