7.2.3 Secondary Objective

Secondary Objective - To assess the safety of simultaneous administration of COVID-19 vaccine with other routinely recommended vaccines among children and adolescent participants.

1) Tables will be produced that summarize each solicited local and systemic reactogenicity event by maximum classification (none, mild, moderate, and severe), as well as by moderate or severe through days 1-7 following COVID-19 vaccination for dose 1 and dose 2 or a booster dose. These tables will have the number and percentage for each classification and will be broken down by concomitant childhood vaccine status (yes/no) by each site and across all sites. (SOM 1, SOM 2 and SOM 3)

2) Tables will be produced that summarize each unsolicited adverse event by maximum classification (none, mild, moderate, and severe), as well as by moderate or severe through days 1-7 following COVID-19 vaccination for dose 1 and dose 2 or a booster dose. These tables will have the number and percentage for each classification and will be broken down by concomitant childhood vaccine status (yes/no) by each site and across all sites. (SOM 4)

3) Tables will be produced that summarize participants experiencing at least one serious adverse event or one AESI through the 29 days after dose 2 or a booster dose. This table will have the number and percentage for each outcome and will be broken down by concomitant childhood vaccine status (yes/no). (SOM5 and SOM6)

The proportions by concomitant vaccine status (yes/no) for secondary outcomes 1 to 6 will be descriptively assessed using an exact Mantel-Haenszel statistic calculated using the Proc Logistic command in SAS at the two-sided alpha 0.05 level. Further details will

be described in the statistical analysis plan. The analysis for exploratory objectives will be described in the statistical analysis plan.

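### The primary safety proportions are planned without confidence intervals, so a zero or sparse SAE or AESI count would not show what rate is excluded; follow-up for dose-1-only children also needs an end point

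*Combined protocol and SAP*

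**What the plan says.** **Method for the primary outcomes.** Section 7.2.2 tabulates each solicited symptom (POM 1) and each unsolicited event (POM 4) by maximum grade: "These tables will have the number and percentage for each classification and will be broken down by each site and across all sites". For POM 2 and POM 3 it gives the number, percentage or proportion of participants with at least one severe, or moderate-to-severe, event. For POM 5 and POM 6: "This table will have the number and percentage for each outcome. Listings with the clinical narratives will also be provided".

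**Precision.** Section 7.1 says that "there will be no formal statistical power or sample size calculation" because the study is observational, and offers nothing in its place. The Protocol Summary describes enrolment as "Up to 320 male or female children and adolescents". No confidence interval is mentioned anywhere in the documents. Section 7 describes its text as a summary and says that a comprehensive SAP will be written.

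**Secondary outcomes, for contrast.** Section 7.2.3 says that the proportions by concomitant vaccine status will be "descriptively assessed using an exact Mantel-Haenszel statistic calculated using the Proc Logistic command in SAS at the two-sided alpha 0.05 level".

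**Population and time window.** Section 7.2.1: "The Study Cohort includes any participant that was enrolled and received at least one dose of a COVID-19 vaccine". POM 5 in section 2 is the "Proportion of participants with an adverse event of special interest through 29 days after dose 2 of COVID-19 vaccine or a booster dose", and POM 6 has the same window. In section 5.1 the visits after Visit 1a are timed from the second vaccine, for example "Visit 3, 28 Days (window days 29-35) after COVID-19 Dose 2".

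**The concern.** The primary objective is to characterize safety, with no hypothesis test and no comparator for the primary outcomes. In such a study, precision tells the reader how much information the sample carries. Section 5.5 expects no significant problem with SAEs and describes the known serious vaccine risks as rare, so the POM 5-6 table may well show 0 or 1. Printed as 0% or 0.3%, that figure invites more reassurance than a few hundred children can give. Narratives describe individual events but cannot show which rates remain compatible with the data.

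The second matter is narrower. A child who enrols at dose 1 and never receives dose 2 belongs to the Study Cohort, but POM 5-6 define the end of observation only from dose 2 or a booster. The child is in the denominator with no stated length of observation.

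**Working it through.** **Inputs**
- Maximum N = 320 (Protocol Summary). The site targets in section 4.3 agree: 60 + 100 + 70 + 90 = 320.
- Confidence level: the plan gives none for POM 1-6. Two-sided 95% is assumed here, in line with the two-sided 0.05 level in section 7.2.3.
- The plan states no precision or power figure, so there is none to reproduce.

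**Zero events.** The exact (Clopper-Pearson) two-sided 95% upper limit solves (1 − p)^n = 0.025, so p = 1 − 0.025^(1/n).
- n = 320: 1 − 0.025^(1/320) = 1.146%, or 1.15%.
- n = 300 (assumed): 1.22%.
- n = 200 (assumed): 1.83%.

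Because 320 is a ceiling, 1.15% is the best case for this method. Other conventions for 0/320 are a one-sided 95% bound of 1 − 0.05^(1/320) = 0.93%, the rule of three at 3/320 = 0.94%, and Wilson at 1.19%. All lie near 1%.

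**Sparse counts at n = 320** (Clopper-Pearson, two-sided 95%)
- 1 event: 0.31% (0.01% to 1.73%).
- 2 events: 0.63% (0.08% to 2.24%).
- 3 events: 0.94% (0.19% to 2.72%).

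**How plausible is zero?** The chance of no events is (1 − p)^320. For assumed true rates of 1%, 0.5% and 0.1% it is about 4%, 20% and 73%.

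**Dose-specific summaries (POM 2-4).** The documents give no split between primary-series and booster enrolment. If 240, 160 or 80 children were assessed for a given dose (assumed), the zero-event upper limit would be 1.53%, 2.28% or 4.51%. These figures do not apply to POM 5-6, which section 7.2.2 does not report dose by dose.

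**Dose-1-only children: the passages side by side**
- In the cohort: section 7.2.1 requires only one dose.
- Early events are kept: Table 1 collects SAEs and AESIs from Visit 1a. Section 4.4 retains data collected before withdrawal. Section 7.2.5 has the safety panel review narratives for all vaccinated participants. Section 5.3 provides for record review throughout the study.
- No end point: Visits 2, 2a, 3 and 4 in Table 1 are timed from the second vaccine, so Visit 1a (days 1-7, +3) is the last contact with a defined date. The windows in section 2, and the surveillance periods in section 5.5, run from dose 2 or a booster. Section 3.1 mentions day 181 without saying from which dose.

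Inclusion is therefore settled, but duration is not.

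**The case against.** **The SAP may supply the intervals.** Section 7 is only a summary, and section 7.2.3 defers further details. This stands as a limit on the claim: the intervals are not stated in section 7, and one cannot conclude that they will never be produced. But section 7.2.3 is specific enough to name a test, a software procedure and an alpha level, while section 7.2.2 gives no measure of uncertainty, and nothing commits the SAP to add one.

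**A reader can compute the limit.** True, since both number and percentage are reported. The omission affects presentation and interpretation; it does not bias the estimates. That makes this an inexpensive improvement rather than a flaw in validity.

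**No power calculation is needed.** Agreed. Its absence from a non-randomized descriptive study is not an error. The gap is the missing precision statement.

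**Intervals on every symptom row are excessive.** This also stands. The argument from sparse counts concerns POM 5-6 and, to a lesser degree, the participant-level summaries. Some POM 1 symptoms are common: section 1 cites injection-site pain in 79% to 94% of adolescents in earlier trials.

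**Two stronger readings are tempting.** A reader might infer that dose-1-only children, and any early event among them, would drop out of POM 5-6. No passage states such an exclusion, and sections 4.4, 7.2.1 and 7.2.5 together point the other way. A reader might also infer that children without diary data would be counted as having no reaction. No passage says so: section 5.1 has staff phone web-diary users about missing values and call paper-diary users at day 7 (+3) to record the diary. The dose-specific denominator is a detail that an analyst would fill in sensibly.

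**Conclusion.** The concern holds in a limited form. Section 7 plans counts and percentages for POM 1-6 with no interval, and section 7.1 offers no statement of precision. At full enrolment, zero events would still be compatible with a true rate of up to 1.15% (exact, two-sided 95%; 0.93% one-sided), and one event with up to 1.73%. With fewer children the limits are wider. These figures rest on the assumed confidence level and on all 320 children contributing to the denominator.

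The dose-1-only matter is a clarification. Such children and their early events stay in, but the end of their observation for POM 5-6 is undefined. The documents do not say how many there will be, so the effect cannot be sized.

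**What to change.** 1. In section 7.2.2, add exact (Clopper-Pearson) two-sided 95% intervals to the all-site proportions for POM 5-6 and for the participant-level POM 2-4 summaries. With POM 2-4 each shown for dose 1, dose 2 and booster, that is 3 × 3 + 2 = 11 intervals. Site tables can stay as number and percentage. Intervals on POM 1 symptom rows are optional; on two rows (total, and moderate or severe) for the 16 symptoms in Tables 4 and 5 and three doses they would add 16 × 2 × 3 = 96.
2. In section 7.1, state that zero events among the maximum of 320 children gives an exact two-sided 95% upper limit of 1.15%, as a best case.
3. Carry both into the comprehensive SAP, or confirm that they are already there.
4. Reconcile section 7.2.1, the POM 5-6 windows and the visit timing in Table 1 by stating the period over which SAEs and AESIs count for a child who receives dose 1 only. Report how many such children there are.

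**Cost.** Items 1 to 3 need a few sentences and one table column, and the results will look less certain. Item 4 needs a sentence and a count, but depending on the period chosen it may also need added contacts or record access: under section 5.5 the release for unscheduled-care records runs only through 29 days after the second dose.
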